9. QUALITATIVE INTERVIEWS

Near the end of the prehabilitation (from the last week of prehabilitation to hospital discharge), a trained co-investigator will conduct semi-structured qualitative interviews of patients and their caregivers (if they are involved in preoperative care).

An interview guide has been developed under qualitative expert consultant guidance. The questions have been grounded in the Behavioral Change Wheel framework to assess factors influencing capability (physical and psychological), opportunity (physical and social), and motivation (reflective and automatic).³⁶ The co-investigator will also ask participants about areas for improvement within our prehabilitation program.

Qualitative data analysis will seek to identify facilitators of and barriers to adhering to our prehabilitation program. We will conduct hybrid deductive and inductive thematic analysis based on the 3 components (capability, opportunity, and motivation) of the Behavioral Change Wheel framework, while also allowing new insights to emerge from the data. The interviews will be audio-recorded and transcribed verbatim. A coding framework to all transcripts will be applied via a collaborative approach through an iterative process. Codes and subsequently derived themes will be refined by the research team.

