- Weekly check-in calls will take place once a week for about 30 minutes per session over 3-4 weeks. During these calls the participant will talk about their goals, discuss personal motivation, and review their progress. They will be asked about any potential adverse events (such as sore muscles or falls).
- A 30 minute telephone interview will take place at the end of the intervention (in weeks 3 or 4). The participant will be asked to provide feedback discussing what parts of the

intervention worked well and what did not. We will use this information for protocol refinement.

The primary outcome is the feasibility of the prehabilitation protocol, defined as the proportion of patients to whom we can deliver an adequate dose ($\geq 50\%$ of the planned sessions) of the 3 core interventions: physical therapy ($\geq 4/8$ sessions), nutrition ($\geq 2/4$ sessions), and meditation ($\geq 2/4$ sessions). Secondary outcomes include 1) adherence to exercise, protein intake and meditation; 2) changes in 5-chair stand time, dominant handgrip strength, patient-centered outcomes, measured using PROMIS scores in physical function, cognitive function, participation in social roles/activities, depression, anxiety, sleep disturbance, pain and fatigue domains at baseline, following completion of the prehabilitation (before surgery), and on postoperative days 30 and 90; 3) clinical outcomes (3-D Confusion Assessment Method,¹ a composite complication score,² length of stay, and 30-day readmission and death); and 4) Postoperative Quality of Recovery Scale³ to be obtained around postoperative day 3; 5) adverse events.

The proposed research will provide necessary information for a larger randomized controlled trial (RCT).

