3. STUDY OBJECTIVES

The **objective** of this pilot study is to evaluate feasibility of a prehabilitation program in frail older adults undergoing major surgery. Our **central hypothesis** is that optimizing risk factors before surgery with a multicomponent prehabilitation protocol will improve postoperative outcomes in high-risk older adults undergoing major elective abdominal, gynecological oncologic, and urologic surgery. By utilizing a patient-centered multicomponent protocol, the most effective intervention strategies of the protocol can be refined for a larger-scale randomized controlled trial. This research has four (4) intervention components: 1) physical therapy; 2) nutrition; 3) meditation; and 4) cognitive behavioral strategies will additionally be utilized to enhance motivation and support self-efficacy. We will accomplish the following two (2) **specific aims**:

3.1 Objective/Aim 1. To evaluate the feasibility of and adherence to the prehabilitation program. We will estimate the duration of preoperative geriatric assessment screening; enrollment rate; feasibility of and adherence to the prehabilitation program; attrition rate; and extent of missing outcome data. We expect that we *will be able to deliver our prehabilitation program to $\geq 50\%$ of patients*.

Feasibility is defined by proportions of enrollment, refusal, and adherence to intervention components as a whole and individually, potential barriers to adherence, and self-reported and objective measures of adherence including diaries, wearable sensors, and physical performance tests. As secondary outcomes, we will collect clinical outcomes (e.g., Postoperative Quality of Recovery Scale, surgical complications, and length of stay) and Patient-Reported Outcomes Measurement Information System (PROMIS) measures.

3.2 Objective/Aim 2. To identify barriers and facilitators of prehabilitation program and refine protocol accordingly. After the prehabilitation program, we will interview patients and their caregivers to identify facilitators, barriers, and areas for improvement. After completing all qualitative interviews, we will refine the intervention components based on participant feedback. This information will inform the design of a future, larger RCT which will target frailty using the most effective intervention components.

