7. STUDY INTERVENTION

All participants will be enrolled in a prehabilitation program that will start 3-4 weeks prior to the date of scheduled surgery. The intervention will target three principal components (physical activity, nutrition, and meditation) and deliver cognitive behavioral interventions

(Table 3). Each intervention has 1) instructional or training components, delivered by our study team, and 2) self-directed components.

Table 3. Multicomponent prehabilitation program and measures of feasibility and adherence for each component

Target	Intervention	Measures of Feasibility or Adherence
Exercise: Increase muscle function	
 • Physical therapy (home, in-person, hybrid or virtual) 
 • By physical therapists • Average two 1-hour individual sessions per week (delivered in patient's home, in-person center, hybrid, or virtual) • Goal: 6-8 total PT sessions • Endurance, strengthening, flexibility • Self-directed exercise 
 • Goal: 30 mins/day x 4 days per week 	
 • Number of sessions delivered (feasibility) 
 • Number of days with ≥ 30 min exercise per self-report diary • Step count from a wearable activity tracker (Fitbit Fitness tracker): provision of weekly feedback based on step count • Change in 5-chair stands and grip strength pre- and post- intervention
Nutrition: Preserve lean body mass (Patients with CKD will be excluded)	
 • Nutrition counseling 
 • By registered dietitian • Average one 1-hour group session per week • Goal: 3-4 total nutrition education sessions • Self-directed protein consumption 
 • Goal: 1-2 ONS (20 gram)/day x 4 days per week 	
 • Number of sessions delivered (feasibility) 
 • Number of ONS consumed per self-report • Change in protein intake per 3-day dietary recall pre- and post- intervention • Change in quadriceps thickness by ultrasound pre- and post- intervention

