8.3 Exploratory Outcomes

For all *other outcomes*, we will measure the following:

- 3-D Confusion Assessment Method³⁴
 - Measurement: proportion of patients who develop delirium according to 3-D Confusion Assessment Method, a clinically validated algorithm of delirium diagnosis, on any of the postoperative days 1 to 3.
 - Range: 0-100%
- Postoperative Quality of Recovery Scale³⁵
 - Measurement: a clinically validated scale that includes physiologic, nociceptive, functional, cognitive, emotional recovery domains assessed as well as overall patient perspective on postoperative day 3.
 - Range: 40-200 (higher values indicate better recovery)
- Comprehensive complication index³⁶
 - Measurement: a composite complication grading system by Clavien-Dindo Classification after an intervention
 - Range: 0-100 (higher values indicate more severe complications)
- Length of stay (time to readiness to discharge)
 - Measurement: number of hospital days from surgery until a patient becomes medically stable for discharge based on clinical notes
 - Range: ≥ 1 day
- 30-day readmission from all causes
 - Measurement: proportion of patients who were readmitted within 30 days of surgery
 - Range: 0-100%
- 30-day mortality from all causes
 - Measurement: proportion of patients who died within 30 days of surgery
 - Range: 0-100%
- 90-day mortality from all causes

- Measurement: proportion of patients who died within 90 days of surgery
 - Range: 0-100%
- Change in PROMIS-CAT score in participation in social roles/activities (4 questions)
 - Measurement: self-reported measure of participation in social roles/activities
 - Range: 0-100 (higher values indicate higher participation)
- Change in PROMIS-CAT score in Anxiety (4 questions)
 - Measurement: self-reported measure of anxiety
 - Range: 0-100 (higher values indicate more anxiety)
- Change in PROMIS-CAT score in Depression (4 questions)
 - Measurement: self-reported measure of depression
 - Range: 0-100 (higher values indicate more depression)
- Change in PROMIS-CAT score in Fatigue (4 questions)
 - Measurement: self-reported measure of fatigue
 - Range: 0-100 (higher values indicate more fatigue)
- Change in PROMIS-CAT score in Pain interference (4 questions)
 - Measurement: self-reported measure of pain interference
 - Range: 0-100 (higher values indicate more interference)
- Change in PROMIS-CAT score in Pain intensity (1 question)
 - Measurement: self-reported measure of pain intensity

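### Three sections give three different windows for the same program interview, and Section 9 permits it after surgery without recording the timing

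*Combined protocol and SAP*

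**What the plan says.** All references are to the combined protocol and SAP.

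- **Section 2 (Overview):** "A 30 minute telephone interview will take place at the end of the intervention (in weeks 3 or 4". Its stated use is: "We will use this information for protocol refinement".
- **Section 3.2 (Aim 2):** "After the prehabilitation program, we will interview patients and their caregivers to identify facilitators, barriers, and areas for improvement". No closing date is given. The next step is: "After completing all qualitative interviews, we will refine the intervention components based on participant feedback".
- **Section 9 (Qualitative Interviews):** the interview belongs near the close of the program, but the parenthesis that defines this runs "from the last week of prehabilitation to hospital discharge". Patients, and caregivers involved in preoperative care, are interviewed, and one coding framework is applied to all transcripts.
- **Section 7 (Study Intervention):** participants enter a "prehabilitation program that will start 3-4 weeks prior to the date of scheduled surgery".
- **Section 8.3 (Exploratory Outcomes):** delirium is counted if present "on any of the postoperative days 1 to 3". Recovery quality is assessed on day 3, and complications are recorded during the hospital stay.
- **Table 5 footnote:** starred end-of-program measures are to be attempted before surgery and taken in hospital only if that did not happen. The interview is not a row in Table 5, so the footnote does not cover it.

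**The concern.** Aim 2 asks what helped or hindered participants in following a program that is over by the time of the operation. Nothing that happens in the operating room or on the ward is needed to answer that, but it can alter the answer. A patient who has recovered smoothly may speak better of the program, and one with a complication may speak worse of it. A patient with acute confusion may give an unreliable account.

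Staff who read Section 2 would schedule a call before admission. Staff who read Section 9 could properly wait until discharge. If both happen, the transcripts are analyzed together, and nobody can later check whether a theme came from the program or from hindsight about the surgery. These interviews are the source for refining the interventions (Section 3.2) and for revising them if the progression criteria fail (Section 12.4).

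**Working it through.** No figure in the plan depends on the interview window, so the check is a comparison of the texts.

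1. **Is it the same interview?** Section 2 asks participants what worked and what did not, for protocol refinement. Sections 3.2 and 9 ask about barriers, facilitators and areas for improvement, and Section 3.2 uses the answers to refine the intervention. The plan describes no second end-of-program interview. Treating all three as one interview is an inference, but the natural one.

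2. **Where does each window fall relative to surgery?** By Section 7 the program occupies the 3-4 weeks before the scheduled date.
   - Section 2: program week 3 or 4, so before surgery.
   - Section 3.2: after the program. Section 5.2 admits patients with as few as 21 days between expected program start and surgery. A 3-week program takes 3 × 7 = 21 days, so the time left before surgery can be 21 − 21 = 0 days.
   - Section 9: from the final program week through the surgical stay, so before or after surgery.

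   The Section 2 and Section 3.2 windows need not overlap at all, and only Section 9 expressly extends into the hospital stay.

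3. **What else happens in the stay?** Delirium screening covers the first three postoperative days, recovery quality is assessed on day 3, and complications are recorded. The Section 9 window includes those days and continues to discharge, so a hospital interview may coincide with the screening days or come later.

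4. **What does Section 9 do about timing?** Its opening words point to the end of the program. It does not say that a pre-surgery interview comes first and hospital second, does not refer to the delirium result, does not record timing relative to surgery, and does not look at themes by timing.

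5. **How many interviews are affected?** The documents give no share, and none is assumed here. One piece of arithmetic shows why the timing should be recorded. Section 11.2 cites 16-24 interviews for thematic saturation and expects 30 patients. If all 30 were interviewed, pre-surgery interviews would fall below 24 once more than 30 − 24 = 6 were postoperative, and below 16 once more than 30 − 16 = 14 were. These are thresholds, not forecasts. Without a recorded date, nobody could tell on which side of them the study ended.

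6. **What is not affected?** The primary outcome (Section 8.1) is a proportion based on sessions delivered. The four progression criteria (Section 12.4) use enrollment, delivery, adherence and day-90 questionnaire completion. None uses interview content.

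**The case against.** The best defense is that Section 9 states a target with an outer limit. It opens by placing the interview near the end of the program and gives the longer span only in parentheses, much as the Table 5 footnote does for other end-of-program measures. With as little as three weeks before surgery, and Aim 2 asking for interviews after the program, a wide window may be a sensible way to avoid losing interviews. This largely stands: a pre-surgery target is implied. What is missing is an explicit order of preference, and the three sections still disagree.

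A reader might also infer more than the documents support:

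- *That some interviews will be held after surgery and will be distorted.* The plan permits postoperative interviews. It does not show that any will occur, and coloring is a reasonable inference rather than a documented fact.
- *That a number of transcripts will be unreliable because of delirium.* This would need an assumed share of postoperative interviews and an assumed delirium rate. It would also treat delirium at any time in the stay as present at the interview. Interviews may fall after the screening days, an interviewer may defer, and caregivers are interviewed too.
- *That late interviews come from the least adherent participants.* Nothing in the documents links the two.

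Finally, hindsight bears more on whether the program seemed worthwhile than on practical barriers such as transport or technology. That is fair, and it limits the effect, but feedback on what worked well remains exposed to it.

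**Conclusion.** The inconsistency is real: Sections 2, 3.2 and 9 give three different windows for what appears to be one interview, and Section 9 allows it after surgery. Such interviews may be colored by the surgical result or by acute confusion. How often this would happen is not stated, so no numerical size is claimed. The consequence is limited to Aim 2 and the refinement of the intervention; the feasibility estimate and the decision criteria for the larger trial stand as they are. This is a minor point, worth making because the correction costs very little. It rests on two assumptions: that the three sections describe the same interview, and that surgery takes place as scheduled after the program.

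**What to change.** Reconcile Sections 2, 3.2 and 9 to one window. Make the interview before the day of surgery the rule, and allow an in-hospital interview only as a fallback, as the Table 5 footnote already does for other end-of-program measures. Do not hold a fallback interview on a day when the 3-D Confusion Assessment Method is positive. That safeguard works only on the days the screen is done, the first three after surgery.

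Record the interview date relative to surgery for each transcript, and note in the report whether the main themes also appear in the pre-surgery interviews.

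The cost is a few words in three sections and one tag per transcript; the delirium screen is already planned. The downside is tighter scheduling in the last program week and possibly a few interviews delayed or lost.

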10. DATA AND SAFETY MONITORING

10.1 Adverse Events

Definition and Classification of Adverse Events

For this study, the following standard adverse event definitions are used:

- Adverse events: Any unfavorable and unintended sign, symptom, or disease temporally associated with the use of the study intervention, regardless of whether it is considered related to the study intervention.
- Serious adverse event: Any adverse event that result in death, life-threatening experience, hospitalization or prolonged hospitalization, persistent or significant disability or incapacity.
- Unanticipated problems: Any experience that 1) is unexpected in terms of nature, severity, or frequency, given the research procedures described in the protocol document and the characteristics of the study population; 2) is related or possibly related to participation in the research; 3) suggests that the research places participants or others at a greater risk of harm than was previously recognized.

Adverse events are graded according to the following scale:

- Mild: An experience that is transient and requires no special treatment. The experience does not generally interfere with usual daily activities.
- Moderate: An experience that is alleviated with simple therapeutic treatments. The experience impacts usual daily activities.
- Severe: An experience that requires therapeutic intervention. The experience interrupts usual daily activities. If hospitalization (or prolongation of hospitalization) is required for treatment, it becomes a severe adverse event.

The study uses the following adverse event attribution scale:

- Not related: The adverse event is clearly not related to the study procedures (i.e., another cause of the event is most plausible and/or a clinically plausible temporal sequence is inconsistent with the onset of the event).
- Possibly related: An event that follows a reasonable temporal sequence from the initiation of study procedures, but that could readily have been produced by a number of other factors.
- Definitively related: The adverse event is clearly related to the study procedures.

10.2 Adverse Event Monitoring

Monitoring adverse events will be primarily performed in two ways: 1) unsolicited report from study interventionists (physical therapist, dietitian, and meditation teacher); and 2) weekly assessments by telephone using a standardized checklist.

- Unsolicited reporting: Any adverse events that occur during the in-person or virtual sessions will be assessed for severity by the study interventionists (in conjunction

with PI or an MD co-investigator). In the event of a serious adverse event, the participant or caregiver will be instructed to contact emergency medical services to receive immediate medical attention. All adverse events will be reported to the PI.

- Standardized assessment: At the beginning of cognitive behavioral intervention telephone calls, co-investigator [name] will assess adverse events using a standardized checklist that includes the following expected adverse events (see below).

Expected Adverse Events

- Exercise: fall or injury (expected risk is low); new or worsening musculoskeletal pain (expected risk is moderate); cardiovascular events including angina, arrhythmia, myocardial infarction, heart failure, or stroke (expected risk is very low); other symptoms including chest pain, dizziness/lightheadedness, dyspnea, palpitation, or syncope (expected risk is low).
- Nutrition: gastrointestinal distress such as diarrhea, nausea, constipation (expected risk is moderate); electrolyte imbalance or dehydration (expected risk is low), renal injury from increased renal solute load (expected risk is very low)³⁸ Meditation: psychological distress (expected risk is very low/rare)³⁹
- Outcome measurement: possibility of incidental finding (such as suicidal ideation) through the Patient-Reported Outcomes Measurement Information System (PROMIS) surveys (expected risk is very low)

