6.1 Baseline Assessment

Once informed e-consent or remote consent is signed, trained research personnel will administer additional measurements that are not collected as part of preoperative assessment. These measurements (provided below) may be conducted 1) during the telephone call during which informed consent is obtained; 2) during a separate call (if

requested by the patient or caregiver); 3) email survey; 4) during an in-person physical therapy session (for gait speed, chair stands, and handgrip strength); or 5) a combination of these modalities.

- Usual walking speed from 4-meter walk (if not already measured)
- Time to complete 5 chair stands (if not already measured)
- Dominant handgrip strength: average of 3 measurements (if not already measured)
- 3-day diet recall (done by telephone)
- PROMIS Profile CAT v1.0 is a 29-item, computer adaptive, patient-reported outcome measure of social roles/activities, anxiety, depression, fatigue, pain interference/intensity, physical function, and sleep disturbance domains (may be done by telephone or email)
- PROMIS v2.0 Cognition CAT is a 12-item, computer adaptive, patient-reported outcome measure of cognitive function domain (may be done by telephone)

PROMIS (available at <https://www.healthmeasures.net/index.php>) is a publicly available, validated system of highly reliable, precise measures of patient-reported health status for physical, mental, and social well-being for general population as well as people with chronic conditions. It is designed to enhance communications between clinicians and patients in diverse clinical and research settings. Computer adaptive test (CAT) allows accurate assessment with a limited number of questions from the PROMIS item bank, thereby reducing participant burden.

6.2 Medical Record Review:

Trained research personnel will obtain the following data from the OMR and record them in REDCap database:

- Demographic information: age, sex, race, ethnicity
- Chronic comorbidities
- Self-reported functional status: ADL, IADL, physical tasks by Nagi and Rosow-Breslau
- Cognitive function: telephone MOCA
- Physical function: gait speed, dominant handgrip strength, and chair stands
- Nutritional status: height, weight, BMI, weight loss in the past year, serum albumin level

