Patients with chronic kidney disease stage 3 or higher will not receive this intervention because high protein intake may accelerate kidney function decline. This will be determined by medical record review (medical history of chronic kidney disease or elevated creatinine value within the last 6 months) and/or lab results obtained before the start of the study intervention.

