8.2 Secondary Outcomes

For *secondary outcomes*, we will measure the following:

- Change in 5-chair stand test (time)
 - Measurement: time to complete 5 chair stands (seconds), post-prehabilitation minus pre-prehabilitation
 - Range: -60 to 60 seconds (higher values indicate worsening performance)
- Change in dominant handgrip strength (kg)
 - Measurement: average of 3 measurements of dominant handgrip strength, post-prehabilitation minus pre-prehabilitation
 - Range: -50 to 50 kg (higher values indicate improved performance)
- Change in protein intake (grams)
 - Measurement: 3-day average protein intake from dietary recall, post-prehabilitation minus pre-prehabilitation
 - Range: -100 to 100 grams (higher values indicate greater intake)
- Adherence to exercise
 - Measurement: proportion of days with ≥ 30 minutes of exercise out of 21-28 days per self-report
 - Range: 0-100% (higher values indicate better adherence)
- Adherence to protein intake
 - Measurement: proportion of oral nutritional supplement consumed over the total number of supplements provided per self-report

- Range: 0-100% (higher values indicate better adherence)
- Adherence to meditation
 - Measurement: proportion of days with ≥ 12 minutes of meditation out of 21-28 days per self-report
 - Range: 0-100% (higher values indicate better adherence)
- Adverse events
 - Measurement: proportion of patients who experience any adverse events per self-report
 - Range: 0-100% (higher values indicate more adverse events)

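### Kidney and electrolyte changes without symptoms are expected supplement harms with no planned detection route, so a zero count would not show their absence

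*Combined protocol and SAP*

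**What the plan says.** The expected harms of the nutrition component in section 10.2 include "electrolyte imbalance or dehydration (expected risk is low), renal injury from increased renal solute load (expected risk is very low". Section 12.1 repeats them as risks to participants and links them to the hyperosmolar content of some supplement formulations. Section 7.2 withholds the supplement in chronic kidney disease stage 3 or higher. It decides this from the record and/or "lab results obtained before the start of the study intervention".

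On detection, section 10.2 says "Monitoring adverse events will be primarily performed in two ways": the first is "unsolicited report from study interventionists (physical therapist, dietitian, and meditation teacher"; the second is "weekly assessments by telephone using a standardized checklist". The Overview describes the weekly call in the same spirit: "They will be asked about any potential adverse events (such as sore muscles or falls".

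Section 10.1 defines an adverse event broadly, so that an unfavorable sign or disease qualifies without a complaint from the participant. Section 8.2 defines the outcome as the "proportion of patients who experience any adverse events per self-report". The record abstraction list in 6.2 has one line that includes a laboratory value: "Nutritional status: height, weight, BMI, weight loss in the past year, serum albumin level". Creatinine and electrolytes are not listed, and Table 5 has no laboratory item at any time point.

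**The concern.** The plan names two harms that can exist purely as laboratory findings, then relies on sources that register what a participant feels, is told, or shows during a session. The outcome in 8.2 is also narrower than the plan's own definition in 10.1. A creatinine rise or abnormal electrolyte found in the chart would meet 10.1 but, if the participant never mentions it, would not count under 8.2.

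What is at stake is how the safety description can be read. The pilot is meant to inform a larger randomized trial, and adverse events go to the safety officer. A reader who sees these harms listed as expected and then sees none reported may take that as evidence about their frequency. For the silent forms it would not be.

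**Working it through.** **The plan's own figure.** The documents give no figure for detecting adverse events. The only relevant number is the sample size of 30 (11.1), the largest possible denominator. It is consistent with its stated purpose: at 21/30 = 70%, the exact 95% interval is 0.506 to 0.853, so the lower limit clears 0.50. (The simple normal formula, 1.96² × 0.7 × 0.3 / 0.2² = 20.2, would give 21; the plan names no method.) Nothing below disturbs this.

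**Routes by which an event could enter the record.**

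| Route | Section | Can it find a silent laboratory change? |
|---|---|---|
| Interventionist reports | 10.2 | No; covers events during sessions |
| Weekly telephone checklist | 10.2 | Only if someone has told the participant |
| Real-time review of serious events | 10.4 | No; acts on events already found |
| Hospital assessment of adverse events | Table 5 | Used only if not done before surgery; 8.2 still scores by self-report |
| Complication index | 8.3 | Postoperative; reflects surgery |
| Pre-intervention kidney check | 7.2 | No; precedes the supplement |
| Record abstraction | 6.2 | No; albumin only |

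No route is a planned check of kidney function or electrolytes after supplementation begins.

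**What a zero count would mean.** Let p be the true event rate and s the share of events that reach the record. The documents give neither, so both are assumptions shown over a range. With n = 30, the chance of no reported event is (1 − p·s)³⁰:

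| p | s = 1 | s = 0.5 | s = 0.1 |
|---|---|---|---|
| 1% | 74% | 86% | 97% |
| 5% | 21% | 47% | 86% |
| 10% | 4% | 21% | 74% |

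The one-sided 95% upper bound on p after zero reports is (1 − 0.05^(1/30)) / s = 9.5% / s. That is 9.5% at s = 1, 19% at s = 0.5, 38% at s = 0.25 and 95% at s = 0.1. For changes that nobody notices, s is effectively 0: zero reports are certain whatever p is, and no bound exists.

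**Denominator.** Thirty is the most that could be exposed. Participants with kidney disease stage 3 or higher get no supplement, and 12.2 limits the hyperosmolar shake to those with significant weight loss or a history of tolerating such products. The rest get a bar or powder. With full detection and zero events, the bound 1 − 0.05^(1/n) is 10.5% for n = 27, 11.7% for n = 24, 13.3% for n = 21 and 18.1% for n = 15. These values of n are illustrative; the documents do not say how many participants will be supplemented, by which product, or with repeat tests.

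**The case against.** The case against giving this weight is substantial.

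- **Other routes exist.** A reader might infer that these harms are sought only by telephone and self-report, and that almost none would be reported whether or not they occur. The documents do not support that. Section 10.2 describes its two routes as the primary ones, interventionists also report, and serious events are reviewed by the PI. Dehydration may be felt, a hospital stay would be noticed, and a participant told of a diagnosis can report it. This stands; the gap is confined to silent changes.
- **The risk is small and mitigated.** The plan rates these harms low or very low, withholds the supplement in kidney disease, and in 12.2 gives rules on fluids, divided or diluted intake and change of product. At a true rate of 1%, zero events would be seen 74% of the time even with perfect detection. This stands, and it means better ascertainment would still leave wide bounds.
- **No renal rate is planned.** Section 8.2 pools all adverse events, and the progression criteria in 12.4 contain no safety criterion. So the documents do not show that a near-zero renal rate would be carried into the trial application.
- **Patients are not left unwatched.** A reader might infer that abnormal values would be missed before surgery. Routine-care results remain visible to the treating team; the gap is in the study's record.
- **The remedy may yield little.** The share with paired values is unknown. The pre-admission testing visit in 7.1 is where the activity tracker may be handed out, which suggests a visit near the start of the program and so a baseline rather than a later value. Section 10.1 has no laboratory criterion, and a single arm cannot separate supplement effects from background abnormalities.

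None of this supplies a planned route for silent changes or removes the mismatch between 10.1 and 8.2.

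**Conclusion.** The point holds in a limited form. The plan lists electrolyte imbalance and renal injury as expected harms and counts signs as adverse events. It nevertheless scores the outcome by self-report and plans no kidney or electrolyte data after the pre-intervention check. Silent laboratory changes therefore cannot be recorded by plan, and a zero count says nothing about them. For events that can be noticed, the 9.5% bound after 0/30 applies only if all are captured and all 30 are exposed. It widens to 19% if half are captured, and further with fewer exposed.

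This rests on reading the listed routes as the whole planned set, and on detection shares that are assumptions. It concerns one part of a secondary outcome in a single-arm pilot without testing. It is a minor, cheap improvement.

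**What to change.** - **8.2:** replace the self-report wording so that an adverse event found by any route, including the medical record, counts. This brings the outcome into line with 10.1.
- **6.2 and 10.2:** for participants given a supplement, abstract from routine care the last creatinine and electrolytes before the first supplement and the last before surgery, where they exist. Fix in advance a standard laboratory definition of a new abnormality and say how it is graded, since the 10.1 scale rests on symptoms, treatment and daily activities. Send such events to the PI and the safety officer.
- **Reporting:** show these events separately from self-reported ones and by supplement type, with the number of participants having both values as the denominator.

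If the sponsor does not want the abstraction, the least that is needed is a statement that the adverse event proportion covers noticed events only.

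The cost is a few REDCap fields filled by staff who already review the record, with no added blood draw or visit. The downsides are a possibly higher adverse event proportion, an unknown and perhaps small share of participants with paired values, and no attribution to the supplement in a single arm.
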